The general goals of the initial phase are to collect initial data to evaluate the frequency and nature of vital sign abnormalities, individually and as a composite, while also socializing the Portrait monitor with clinicians. Blinded data collected in this phase will be recorded for subsequent analysis and used to design alarm thresholds that will identify clinically meaningful events with few "false alarms." The tentative goal will be an average of several alerts per day per monitored patient. Clinicians will be completely blinded during this phase.

Primary Aim. Collect blinded data to evaluate the frequency and duration of vital sign abnormalities detected by the GE Portrait monitor, and the fraction that are detected clinically and the extent to which they overlap.

Secondary Aim 1. Design clinically meaningful alerts based on the data collected and abnormalities detected while avoiding false alerts.

Secondary Aim 2. Determine the frequency of the alerts, using criteria determined in Aim 1.

Secondary Aim 3. Determine the fraction of potentially serious vital sign abnormalities detected by GE Portrait monitoring that are also detected by clinicians using routine every four-hour monitoring and vice versa.

Second phase

In the second phase, patients will be randomized to blinded or unblinded GE Portrait monitoring. We will determine whether unblinded monitoring reduces the cumulative duration of vital sign abnormalities. We will also assess the extent to which clinicians find alerts to be useful versus distracting.

Primary Aim. Determine whether patients with unblinded continuous ward monitoring with the GE Portrait Mobile Monitoring Solution experience less time with vital sign abnormalities as defined in the initial phase of the study. Specifically, we will test the primary hypothesis that the cumulative duration of vital sign abnormalities (using criteria determined in Phase 1) is shorter with unblinded than blinded GE Portrait monitoring in patients recovering from major noncardiac surgery.

Secondary Aim. Evaluate the extent to which clinicians believe that alerts from the GE Portrait monitor are clinically meaningful.

Third phase

In this phase, we will refine the alert thresholds developed Phase 1 if necessary. Again, we will estimate the extent to which unblinded monitoring reduces the cumulative duration

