of vital sign abnormalities. And on an exploratory basis, we will determine whether unblinded monitoring reduces a composite of interventions for vital sign abnormalities. These results will provide guidance for a future full trial with "hard" outcomes.

Primary Aim. Determine whether unblinded continuous ward monitoring with the GE Portrait Mobile Monitoring Solution reduces vital sign abnormalities. Specifically, we will test the primary hypothesis that the cumulative duration of vital sign abnormalities (using criteria refined in Phase 2) is shorter with unblinded than blinded GE Portrait monitoring in patients recovering from major noncardiac surgery.

Exploratory Aim 1. Determine whether continuous ward saturation, ventilation, and pulse rate monitoring reduces a collapsed composite of substantive respiratory interventions. Components of the composite will be:

- Naloxone administration;
- Insertion of oral or nasal airways;
- Non-invasive ventilatory support including for bag and mask ventilation;
- Rapid Response Team activation;
- Unplanned ICU transfer;
- Unplanned intubation;
- CPR;
- o Death.

Methods

We anticipate enrolling patients cared for in 2-4 designated surgical wards at the Cleveland Clinic Main Campus. The study will be restricted to designated wards because active nursing engagement and training will be required. Ward assignments are largely determined by bed availability and therefore cannot be reliably predicted preoperatively. Consent will therefore be obtained shortly after patients are admitted to one of the participating wards. A screening log will be maintained.

There will be no restriction on sex, race, or ethnicity; all qualifying patients will be asked to consider the study. Our prospective cohort study will be conducted with all necessary regulatory approvals and will be registered on ClinicalTrials.gov. A full statistical analysis plan will be developed before any data are evaluated. Reporting will be consistent with the CONSORT guidelines. The project will be managed by a Steering Committee consisting of study leaders who are not involved in day-to-day enrollment and data acquisition.

We plan to enroll between 100 patients in the first phase, 150 patients in the second phase, and 250 in the third phase. We expect that patient enrollment for each will last between 2 and 4 months. Data analysis for each phase and consideration of thresholds will likely require several months between phases 1 and 2, and between

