phases 2 and 3. Data cleaning and analysis for phase 3 will require at least several months.

Subject selection

Consenting patients will be **eligible** if they:

- 1. Are admitted to one of the wards equipped with the GE Portrait Mobile Monitoring Solution;
- 2. Are \geq 18 years old;
- 3. Are designated American Society of Anesthesiologists physical status 1-4;
- 4. Had major noncardiac surgery lasting at least 1.5 hours;
- 5. Are expected to remain hospitalized at least two postoperative nights;
- 6. Had general anesthesia with or without neuraxial anesthesia.

Patients will be ineligible if they:

- 1. Have language, vision, or hearing impairments that may compromise continuous monitoring;
- 2. Are designated Do Not Resuscitate, hospice, or receiving end of life care;
- 3. Have previously participated in the study.
- 4. Patients who have "Implantable Minute Ventilation Rate Responsive Pacemakers"

Protocol

In all cases, good judgement will predominate. Clinicians should always act in their patients' best interests, irrespective of this protocol.

Patients will be enrolled postoperatively after admission to a surgical ward. Consequently, anesthetic management will not be controlled. Postoperative analgesia will be entirely at clinical discretion and can include field, plane, and nerve blocks. No aspect of clinical care is prescribed by this protocol.

All patients will have normal vital sign assessments by nurses at 4-hour intervals per Cleveland Clinic routine, and more often as clinically indicated. Clinicians may make any interventions they believe necessary. *Thus, no patients will be denied routine monitoring and management.* Participating patients will have continuous pulse oximetry, ventilation, and heart rate monitoring *in addition to all routine vital signs* as tolerated for 72 postoperative hours using the GE Portrait ward monitoring solution (Fig. 5, Appendix 1). Clinicians will be carefully trained not to rely on measurements from the GE Portrait, and to always confirm concerning values with conventional monitors and physical assessment. Details of network communication are provided in Appendix 2.

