The patient units are powered by small rechargeable batteries that last at least 24 hours. Investigators will swap depleted batteries for fully charged ones daily. Data from the patient module will be transmitted to a small hub in each patient's room using MBAN (similar to Bluetooth) proprietary secure communication. The hub normally rests in a charging dock, and can be taken with patients if they care to leave their rooms. The hub retransmits monitor data in real time via the hospital's secure "internal" Wi-Fi system to display screens in clinical areas and to the Department of Outcomes Research, which is a double-locked card-key controlled location restricted to Departmental investigators.

During the initial phase of the study, all monitoring will be clinician-blinded. That is, recorded for *post hoc* analysis. During the subsequent phases of the study, patients will be randomly assigned to unblinded versus blinded monitoring. In both cases, information from the GE Portrait Monitor will be recorded, but will be available to clinicians only when patients are assigned to unblinded monitoring. Randomization will be based on computer-generated codes, in random blocks of 4-8 patients, without stratification. A web-based system will be accessed by investigators after consent is obtained. Allocation will therefore be concealed as long as practical.

Measurements

Baseline demographic and morphometric characteristics will be recorded, including height, weight, and sex. Elements of the STOP-BANG sleep apnea questionnaire will be recorded.^{7,41,42} Cardiopulmonary risks will be recorded, including hypertension requiring treatment, diabetes requiring oral medications or insulin, history of previous myocardial infarction, congestive heart failure, chronic obstructive pulmonary disease, current smoking status, and pack-years of smoking history. Cardiovascular and pulmonary medications will be similarly recorded by category, including beta blockers,

angiotensin converting enzyme inhibitors, angiotensin receptor blockers, calcium channel blockers, statins, bronchodilators, and inhaled steroids.

Baseline laboratory values (within 30 days before surgery) will be recorded on an as-available basis, including albumin, BNP, NT-ProBNP, troponin, and FEV1. Results of sleep studies will be recorded.

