We plan for 100 patients in the first phase, 150 in phase 2, and 250 in phase 3. When comparing groups on continuous outcomes for Phases 1, 2 and 3, respectively, we will have 90% power at the 0.05 significance level to detect a difference in means of 0.66, 0.53 and 0.41. When comparing groups on binary outcomes such as the collapsed composite outcome in Phase III we will have 90% power at the 0.05 significance level to detect relative risks of 0.10, 0.30 or 0.45 or stronger given corresponding control group incidences of 0.10, 0.20 or 0.30.

Limitations

Active participation and engagement from ward clinicians will be essential, including nurses, hospitalists, anesthesiologist members of the acute pain team, and surgeons. To that end, key personnel from each specialty are co-investigators and have agreed to champion the project, including the Associate Chief Nursing Officer for Nursing Research and a senior member of a relevant surgical department. Thus, while considerable effort will be required, we anticipate high engagement from participating clinicians.

Our experience with four other continuous ward monitoring systems is that most patients tolerate monitoring well, but there are inevitably patients who drop out of monitoring studies. And even for those who remain in a study, there are often gaps of varying duration. Our experience is that paying patients, even a trivial amount, much improves cooperation with monitoring. The GE Portrait system is untethered and small, and therefore should be relatively well tolerated.

Clinical interventions are multifactorial and usually based on many factors. It will thus not always be possible to reliably attribute a particular intervention to a GE Portrait alert. Nonetheless, by personally asking clinicians in real time, we will reasonably be able to estimate whether the GE Portrait alert was the initial prompt for further evaluation and eventual treatment.

Human Subjects Protection

In all cases, good judgement will predominate. Clinicians should always act in their patients' best interests, irrespective of this protocol.

The study will be conducted with IRB approval and written patient consent. The study will be restricted to designated wards because active nursing engagement and training will be required. Furthermore, the GE monitoring system will only be available in selected wards.

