The study will be guided by a Steering Committee that will review enrollment, protocol compliance, data quality, and adverse events. Safety will be evaluated after each pilot phase, and more often if deemed necessary.

Patients will be paid \$1/hour of successful monitoring time, to a maximum of 72 postoperative hours. Our intent is to pay patients for monitoring time, even if unsuccessful because of technical difficulties, but not for periods when they electively remove or disable the monitors. Payment will be made by check about 8 weeks after discharge.

The GE Portrait ward monitoring system is not yet FDA cleared. We thus request a non-significant-risk device exemption from the IRB. The basis for our request is:

- 1) The device itself is battery powered, external, and presumably inherently riskfree. Detailed documentation of design and process control, and electrical safety is provided in Appendix 1;
- 2) Clinical staff will never make clinical decision based on values from the GE Portrait monitor. Any potential abnormalities will be confirmed with convention monitors and clinical examinations. To the extent that alerts are unfounded, they will disrupt nurses but not harm patients. Based on the initial blinded portion of the proposed pilot, alert thresholds will be designed to occur no more often than an average of twice per day per patient.
- 3) True alerts (confirmed with conventional monitors) will potentially improve care by allowing clinicians to intervene and perhaps prevent serious cardiorespiratory complications.
- 4) Continuous monitoring data will be transmitted with a secure proprietary communication algorithm (similar to Bluetooth) to a hub in patient rooms, and from there to the Clinic's internal secure Wi-Fi system. Connections to the Clinic's data system will be made with full approval from the responsible HIPAA data security team. Ward monitoring data will thus be as secure as other clinical data.

The major risk to patients will be discomfort from wearing the GE Portrait Mobile Monitoring Solution. However, the level of discomfort will be slight since the system consists of a small light-weight battery powered unit and several "stick-on" pads. Of course, patients will always have the prerogative to remove the system themselves should it become burdensome.

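### Phases 2 and 3: randomisation is conditional on consent only, so patients whose monitor never yields usable data can be randomised and lost after investigators know the arm

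*Combined protocol and SAP*

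**What the plan says.** All references are to the combined protocol and SAP.

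- **When the arm is revealed (Protocol).** "A web-based system will be accessed by investigators after consent is obtained. Allocation will therefore be concealed as long as practical". No device condition or time point is attached to either sentence.
- **When consent is taken (Methods).** "Consent will therefore be obtained shortly after patients are admitted to one of the participating wards".
- **Eligibility concerning the device (Subject selection).** The only such inclusion item is about the ward: "Are admitted to one of the wards equipped with the GE Portrait Mobile Monitoring Solution". One exclusion covers a type of pacemaker. Nothing asks for a working or accepted monitor on the patient.
- **Primary hypothesis (Specific Aims, Second phase).** "the cumulative duration of vital sign abnormalities (using criteria determined in Phase 1) is shorter with unblinded than blinded GE Portrait monitoring". Phase 3 repeats it with refined criteria. In both arms the data come from the Portrait recording; the arms differ in whether clinicians can see it (Protocol).
- **Expected losses.** Limitations accepts that "there are inevitably patients who drop out of monitoring studies" and that recordings often have gaps. Human Subjects Protection adds that "patients will always have the prerogative to remove the system themselves should it become burdensome". No rate is given.
- **Analysis (Data analysis, Phase II and Phase III).** A t-test or Wilcoxon-Mann-Whitney test. No analysis population, minimum monitored time or missing-data rule is stated. Methods promises a full statistical analysis plan before data are evaluated.

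**The concern.** The Portrait monitor is both the intervention and the measuring instrument. A randomised patient who refuses the sensors at the bedside, takes them off at once or never produces a signal has received neither monitoring strategy and has no primary outcome.

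If that failure comes before randomisation, it is a screen failure and cannot depend on the arm. If it comes afterwards, it is missing outcome data in a comparison where investigators know the allocation. They open the randomisation system and also keep the devices running through daily battery changes. Clinicians see monitor data only in the unblinded arm, and alerts there bring an investigator to the caregiver, typically within 15 minutes. An absent signal is therefore more likely to be noticed and corrected in one arm than in the other. This mechanism is plausible; the documents do not show that it operates.

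At stake are some power and, if loss differs by arm, the validity of the primary comparison. Phase 1 has no randomised groups and is not affected. The exploratory composite of interventions does not rest on the recording alone and is less exposed.

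**Working it through.** **1. Reproduce the stated figures.** Sample Size Considerations gives 150 and 250 patients, 90% power, significance level 0.05, and detectable differences in means of 0.53 and 0.41. Sidedness, units and allocation ratio are not stated. I assume two-sided testing, SD units and 1:1 allocation, so n = 75 and 125 per arm.

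Detectable difference = (1.960 + 1.282) × √(2/n)

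- Phase 2: 3.242 × √(2/75) = 0.529
- Phase 3: 3.242 × √(2/125) = 0.410

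Both agree with the plan, but only if every randomised patient supplies the outcome. No allowance for loss is included.

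**2. Patients without an outcome.** The documents give no never-usable rate. I assume 5% to 15%.

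- Phase 2: 150 × 0.05 = 7.5 and 150 × 0.15 = 22.5, so 8 to 23
- Phase 3: 250 × 0.05 = 12.5 and 250 × 0.15 = 37.5, so 13 to 38

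**3. Effect on precision.** The detectable difference scales with 1/√(1 − loss). At 10% loss the factor is 1/√0.9 = 1.054.

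- Phase 2: 0.53 × 1.054 = 0.56
- Phase 3: 0.41 × 1.054 = 0.43

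Power at the originally stated differences (normal approximation):

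| Assumed loss | Phase 2 | Phase 3 |
|---|---|---|
| 5% | 88.6% | 88.5% |
| 10% | 86.8% | 86.8% |
| 15% | 84.9% | 84.8% |

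**4. When bias arises.** Suppose there is no true effect, patients without data are excluded, and their true outcome would have been k SD worse than their arm's mean. The mean among those retained shifts by −loss × k/(1 − loss) in each arm.

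- Loss of 10% in both arms: the shifts cancel, the difference is 0 and type I error stays at 5%.
- Loss of 5% in one arm and 15% in the other: difference = k × (0.15/0.85 − 0.05/0.95) = 0.124k. For k = 0.5 to 1.0 this is 0.06 to 0.12 SD. Two-sided type I error becomes 6.5% to 11.1% with 150 patients and 7.5% to 15.3% with 250.

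Every input to the second case is assumed. It shows that bias needs a difference in loss between arms; it does not estimate what will happen.

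**The case against.** The strongest reply is that the text is silent on order, not wrong about it. Attaching the sensors first and then opening the web system would comply fully with what is written. A reader might infer that the protocol reveals the arm and applies the device afterwards. No section says so. A reader might also infer that the stated wish to conceal allocation for as long as is practical has not been met. That does not follow: concealment is tied to consent and protects against selection at enrolment, and whether further delay is practical is a matter of judgement. Both objections stand.

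Three more stand in part.

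- The remarks on dropout and removal mainly describe loss during monitoring, which a check at the start would not prevent. No section reports patients who never yield a signal.
- There are mitigating features. Both arms wear the same device, patients are paid for monitored time, Limitations reports that most tolerate monitoring well, and Phase 1 can measure early failure before anyone is randomised.
- A reader might suppose that a patient without data would be scored as zero minutes of abnormality. No text does this. The raw saturation summaries use minutes per monitored hour, which is undefined without monitoring. The Phase II test states no denominator, so the handling is open.

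Two replies carry less weight. The promised analysis plan can set missing-data rules, but it cannot conceal an arm already revealed or recover signals never recorded. And a pilot may reasonably randomise everyone who consents, but a patient with no signal experiences neither monitoring strategy, so little generalisability is lost by screening such patients out.

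**Conclusion.** The point holds as a gap in the specified order of procedures. Consent is the only stated condition for opening the randomisation system, and nothing says whether a working monitor must come first. The plan thus permits, without requiring, a sequence in which never-started patients enter the randomised set with the arm known.

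The cost in precision is modest: at an assumed 10% loss, about 0.56 instead of 0.53 in Phase 2 and 0.43 instead of 0.41 in Phase 3. This rests on two-sided testing, SD units, 1:1 allocation and a loss rate that the documents do not supply. Bias is possible but not demonstrated, and requires loss that differs by arm. The change below is a worthwhile, inexpensive improvement, not the repair of a demonstrated failure of concealment.

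**What to change.** In Phases 2 and 3, have investigators open the web system only after three steps:

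1. consent;
2. sensor attachment;
3. a brief check, with clinicians still blinded, that saturation, respiratory rate and pulse reach the hub.

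Make the check the last eligibility item. Enter failures as not randomised in the screening log that Methods already provides for, and count outcome time from randomisation.

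The costs are a short delay, some investigator time to attach, verify and then randomise, and slightly less outcome time. If the check took 30 minutes, that would be 0.5/72 = 0.7% of the full 72-hour window, and somewhat more of the part spent on the ward. Results would apply to patients who initially accept the monitor; early non-acceptance can still be reported from Phase 1 and the screening log.

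Two limits should be stated. The change does not deal with later removals or gaps. Those need their own rules: an analysis population, a minimum monitored time or a per-monitored-hour outcome, and a missing-data sensitivity analysis. Nor should the check period be relied on as a baseline for the outcome: most of the abnormalities defined for the Phase 1 primary aim need 30 continuous minutes, so a brief check could hardly register one.

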Anesthesia will be characterized as general, neuraxial, or combined. Use of peripheral plane and nerve blocks will also be recorded. Routine anesthetic variables will be recorded including time-weighted average volatile anesthetic partial pressure, fluid type and volume, estimated blood loss, and transfusions. Postoperative opioids will be converted to morphine sulphate equivalents (Appendix 3).⁴³ On an as-available basis, we will record hemoglobin and troponin concentrations obtained during the initial four postoperative days.

Outcome definitions

Initial phase

Primary Aim. As in previous studies,^{5,44} we will present vital sign abnormalities as continuous functions of duration and severity of vital sign abnormalities. An advantage of this approach is that we do not need to pre-define thresholds and will instead present various combinations of durations and thresholds for bradycardia, tachycardia, saturation, and respiratory rate. See Figure 2 as an example for saturation.

However, to evaluate clinical detection of vital sign abnormalities we need to define thresholds. We will consider the following thresholds and continuous durations to be clinically meaningful: A) saturation <90% for 30 minutes; B) heart rate >110 beats/min for 30 minutes; C heart rate <40 beats/min for 15 minutes; D) respiratory rate <6/minute for 30 minutes or <3/minute for 10 minutes; and, E) respiratory rate >20 for 30 minutes. Because physiological signals are inherently noisy, all values will be electronically smoothed to some degree, but raw data summaries will be used as a cross-check (see Data Analysis for details).

Secondary Aim 2. Continuous ward monitoring with the GE Portrait Mobile Monitoring Solution detects a composite of vital sign abnormalities more often than routine nursing vital signs at 4-hour intervals in noncardiac surgical patients over the initial 72 postoperative hours in the surgical ward while hospitalized. Components of the composite will be: A) saturation <85% for \geq 60 seconds,⁵ B) pulse rate <130 beats/min for 30 secs,⁴⁵ C) pulse rate <40 beats/min for 30 secs,⁴⁶ D) low respiratory rate <4/minute for 30 secs E) high respiratory rate >25 for 120 secs, and, F) apnea >120 secs.

Phases 2 and 3

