An investigator will ask the relevant clinician (usually a nurse) to rate each alert as clinically meaningful or not. Specifically, clinicians will be asked to rate alerts as "critical," "important," "informative," or "false or distracting." The terms will intentionally not be further defined, thereby allowing caregivers to determine themselves the extent to which

a given alert was helpful or not. Caregivers will be queried in person shortly after each alert, typically within 15 minutes. The thresholds, determined in the initial phase, will be set to generate an average of about 2 alerts per patient per day — and therefore will not be onerous for clinicians.

We will also evaluate the following interventions in our composite: 1) drugs that slow or speed heart rate; 2) administration of bronchodilators; 3) initiating or increasing oxygen administration (increment in oxygen concentration, flow rate, or administration mode); 4) mask, CPAP or high-flow oxygen (e.g., 60 L/min) respiratory support; 5) nursing requests for physician evaluation; 6) activation of a Rapid Response Team; 7) intubation; 8) cardiopulmonary arrest; and, 8) transfer to a monitored ward or critical care unit. Investigators, in consultation with clinicians, will determine which interventions were made, and whether they were prompted by GE Portrait alerts.

Data management

Study data will be entered into a custom secure Redcap database that will be maintained on secure Cleveland Clinic servers and backed up to remote sites nightly. The system will record who accessed the randomization system and when it was accessed. The database will include appropriate logic and range checks, and track all changes.

Most data will be obtained directly from the GE Portrait monitor and electronic records. Other values will be entered manually directly entered into Redcap from source documents or initially recorded on case report forms for subsequent transfer to Redcap.

Data analysis

Pulse oximetry data are difficult to analyze due to the high degree of variability in saturation that occurs within each patient. We will thus use an approach similar to our previous analysis.⁵ On one hand, patients might experience frequent, short episodes of more severe hypoxemia, while on the other hand, average SpO₂ may linger within slightly abnormal or dangerous territory for hours. The latter is difficult to ascertain from the raw SpO₂ data. We will therefore consider both raw and smoothed (or filtered) SpO₂ data.

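### No pre-randomization saturation, heart rate, respiratory rate or oxygen support is listed for capture, and the Phase II and III primary comparison is unadjusted, at a possible cost in precision

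*Combined protocol and SAP*

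**What the plan says.** All places are in the combined protocol and SAP.

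- **Measurements.** "Baseline demographic and morphometric characteristics will be recorded, including height, weight, and sex". The section then lists STOP-BANG elements, cardiopulmonary history (including COPD, heart failure and smoking), medication classes, laboratory values and FEV1 as available, sleep studies, and anesthetic variables. Saturation, heart rate, respiratory rate and oxygen support before randomization do not appear.
- **Outcome definitions, Initial phase, Primary Aim.** "We will consider the following thresholds and continuous durations to be clinically meaningful", followed by absolute limits such as saturation below 90% for 30 minutes. The Phase II criteria are to be set from Phase I results.
- **Specific Aims, Second and Third phase.** The primary outcome is the cumulative duration of vital sign abnormalities.
- **Data analysis, Phases II and III, Primary Aim.** The arms are compared by a two-group parametric or rank test. No covariate is named.
- **Protocol.** "All patients will have normal vital sign assessments by nurses at 4-hour intervals per Cleveland Clinic routine". Data management names electronic records as a main data source.
- **Outcome definitions, Phases 2 and 3.** Oxygen appears only as an intervention: "initiating or increasing oxygen administration".
- **Randomization (Protocol).** "Randomization will be based on computer-generated codes, in random blocks of 4-8 patients, without stratification". It takes place after consent on the ward, and no monitored run-in is described.

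**The concern.** The outcome counts time beyond fixed limits of three signs. Patients of ASA status 1–4 are eligible, and no exclusion covers chronic lung disease or home oxygen. A patient who arrives with low saturation or a fast respiratory rate can therefore accrue abnormal time in either arm.

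Abnormal time is also likely to be concentrated in a minority. In the earlier blinded cohort described in the background, 20% of patients averaged 10 minutes per hour below 90%. With unstratified allocation of 150 or 250 patients, a few such patients can fall unevenly between arms by chance. Nothing on the baseline list would show this directly.

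The listed covariates are indirect substitutes. The protocol's own background reports that STOP-BANG was not associated with the amount of desaturation, and that baseline and procedural characteristics predicted respiratory events with an area under the curve of only 0.7. Readings taken after randomization cannot fill the gap, because unblinded alerts may change both the signs and oxygen use.

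At stake are precision that may be cheap to obtain, a check on chance imbalance, and the ability to describe how abnormal patients were at entry. The last of these also bears on the future trial that this pilot is meant to inform.

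**Working it through.** **Inputs**

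- Sample size, from Sample Size Considerations: "We plan for 100 patients in the first phase, 150 in phase 2, and 250 in phase 3".
- Power statement, from the same section: "we will have 90% power at the 0.05 significance level to detect a difference in means of 0.66, 0.53 and 0.41". Sidedness, units and SD are not given. I assume a two-sided test and differences in SD units (SD = 1).
- Allocation ratio: not stated. I assume 1:1, so 75 per arm in Phase 2 and 125 per arm in Phase 3.
- Correlation r between the baseline values and the outcome: not in the documents. I assume 0.1 to 0.6. With several covariates, r stands for the multiple correlation.

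**Step 1: reproduce the plan's figures.** The detectable difference is (1.960 + 1.282) × √(2/n).

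- Phase 2: 3.242 × √(2/75) = 0.529. The exact t calculation gives 0.533. The plan says 0.53.
- Phase 3: 3.242 × √(2/125) = 0.410. The exact t calculation gives 0.412. The plan says 0.41.

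The stated figures are reproduced if they are in SD units. They assume no covariate.

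**Step 2: effect of adjustment.** In a linear model the residual SD is √(1 − r²), and the detectable difference shrinks by the same factor. Starting from 0.533 and 0.412:

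| Assumed r | √(1 − r²) | Variance removed | Phase 2 (SD) | Phase 3 (SD) |
|---|---|---|---|---|
| 0.1 | 0.995 | 1% | 0.530 | 0.410 |
| 0.2 | 0.980 | 4% | 0.522 | 0.404 |
| 0.3 | 0.954 | 9% | 0.508 | 0.393 |
| 0.5 | 0.866 | 25% | 0.462 | 0.357 |
| 0.6 | 0.800 | 36% | 0.426 | 0.330 |

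**Step 3: the same result as power.** Power at the stated 0.53 and 0.41 is Φ(d√(n/2)/√(1 − r²) − 1.960). Phase 2, r = 0.5: 0.53 × √37.5 / 0.866 − 1.960 = 1.79, so power is 96%.

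| Assumed r | Power, Phase 2 | Power, Phase 3 |
|---|---|---|
| 0 | 90.1% | 90.0% |
| 0.1 | 90.4% | 90.3% |
| 0.3 | 92.5% | 92.5% |
| 0.5 | 96.3% | 96.3% |
| 0.6 | 98.2% | 98.2% |

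**Step 4: limits of the calculation.** The whole gain comes from adjustment. Recording the values while keeping the unadjusted test gains no precision. The √(1 − r²) rule belongs to linear ANCOVA; for a skewed duration or a rank-based analysis it is only a guide.

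**The case against.** The strongest reply is that the gain may be close to nothing.

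- **Weak correlation.** The protocol reports that 4-hourly nurse checks missed 90% of serious hypoxemic episodes, that saturation varies greatly within a patient, and that desaturation is hard to predict. A single charted reading soon after surgery, perhaps on oxygen, may correlate weakly with abnormal time over the following days. At r = 0.1 to 0.2 the detectable difference hardly moves. This stands, and it is why the range starts at 0.1.
- **Not a baseline of the outcome.** A spot value is not a baseline of cumulative duration, which would need a monitored period before randomization. This also stands.
- **The list is open.** It is introduced as non-exhaustive, and Methods promises a full analysis plan before data are evaluated. This stands in part: the values could still be added, but neither their capture nor their use is planned now.

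Four stronger readings are tempting and are not supported:

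1. *A reader might infer that the baseline values are lost, or that chronic abnormality cannot be distinguished at all.* Nurses take vital signs routinely and electronic records are a named source, so later retrieval is probably possible. COPD, heart failure, smoking, sleep studies and FEV1 where available give partial information.
2. *A reader might infer bias.* Randomization balances prior abnormality in expectation, and the stated hypothesis concerns total abnormal time, not new abnormal time.
3. *A reader might infer that the oxygen intervention cannot be scored.* It is defined as an increment, so its reference is the level just before the change, not the level before randomization. It also belongs to an intervention composite, not to the primary outcome.
4. *A reader might want a sensitivity analysis without patients already beyond a limit at entry.* The Phase I limits require sustained abnormality, such as 30 minutes, which one spot reading cannot show.

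**Conclusion.** The omission is real. No pre-randomization value of the three signs that form the primary outcome, and no oxygen support, is listed for capture, and the primary comparison uses no covariate. The consequence is limited to precision, a check for chance imbalance, and interpretation. The comparison is not biased by it, and the sample size figures are not wrong because of it.

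The gain from adjustment runs from negligible (r = 0.1) to a fall in the detectable difference from 0.53 to 0.43 SD in Phase 2 and from 0.41 to 0.33 SD in Phase 3 (r = 0.6). This rests on an assumed correlation, 1:1 allocation, a two-sided test, differences in SD units, and a linear model. The documents do not favor the upper end of the range. That usable readings and oxygen levels are charted before randomization is an inference from the routine nursing schedule. The change is worth making because it is cheap, not because the gain is assured.

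**What to change.** 1. **Capture.** Add to Measurements the last charted saturation, heart rate, respiratory rate and oxygen device or flow before randomization, and preoperative room-air saturation where charted, all from the electronic record. Define the time window.
2. **Description.** Tabulate these values by arm in Phases II and III.
3. **Analysis.** In the Phase II and III primary comparisons, prespecify them as covariates, with a method suited to a skewed duration: for example ANCOVA on a transformed outcome, or a covariate-adjusted ordinal or rank-based model. State the effect measure that goes with the chosen method.
4. **Missing values.** State a rule in advance for missing baseline values.
5. **No exclusion analysis.** Do not define a subgroup or sensitivity analysis by a single reading beyond a limit.
6. **Reporting.** Report the observed baseline-outcome correlation, so that the future trial can be sized with it.

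The cost is a short record extract and some missing values, most likely among the preoperative readings. No extra patient contact is needed and the sample size does not change.
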